3.3 Study Population

For entry into the study, the following criteria MUST be met prior to dosing on Day 1.

No exceptions will be granted.

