 2. An increase \geq 50% in the size of previously involved sites $>$ 6 months after completing planned therapy.
- iii. Definition of Refractory FL
 1. $<$ 50% decrease in lesion size after planned therapy
 2. The appearance of new lesions during therapy or $<$ 6 months after completion of planned therapy
 3. An increase of \geq 50% in the size of previously involved sites during therapy or $<$ 6 months after completion of planned therapy

g. Melanoma (MEL) Subjects with progressive or recurrent disease (per RECIST v1.1) during or after anti-PD-1 or anti-PD-L1 therapy:

- i. Subjects must have known BRAF V600 mutation status or consent to BRAF V600 mutation testing per local institutional standards during the Screening Period.
- ii. Histologically confirmed unresectable Stage 3 or Stage 4 melanoma as per American Joint Committee on Cancer (AJCC) staging system
- iii. Must have received anti-PD-1/anti-PD-L1 with or without anti-CTLA4 treatment as most recent therapy and have progressed during or after therapy.
- iv. The last dose of prior anti-PD-1/anti-PD-L1 treatment \geq 28 days from initiation of study therapy.
- v. No more than 25% of MEL subjects (5 during stage 1 and 5 during stage 2 of cohort expansion) will be enrolled with primary refractory disease (ie, a BOR of PD per RECIST v1.1). The remaining subjects in the cohort will be subjects with relapsed disease (ie, SD, PR or CR but progressing on therapy).

h. Melanoma (MEL) Subjects with PD-L1 negative

- i. Fresh, pre-treatment biopsies are required.
- ii. Subjects must have known BRAF V600 mutation status or consent to BRAF V600 mutation testing per local institutional standards during the Screening Period.
- iii. Histologically confirmed unresectable Stage 3 or Stage 4 melanoma as per American Joint Committee on Cancer (AJCC) staging system
- iv. Treatment naive subjects (ie, no prior systemic anticancer therapy for unresectable or metastatic melanoma).
 1. Note: Prior adjuvant or neoadjuvant melanoma therapy is permitted if it was completed at least 4 weeks or 5 half-life times (whichever is shorter) prior to randomization and all related adverse events have either returned to baseline or stabilized. However, no prior therapy with immune checkpoint inhibitors (eg, anti-PD-1, anti-PD-L1, anti LAG 3 and anti-CTLA4); immune costimulatory molecules (eg, anti-CD137, anti-OX40, anti GITR); anti-cancer vaccines (eg, Provenge, MAGE-3); or other immune modulating monoclonal antibodies is permitted.

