- Hormonal methods of contraception including combined oral contraceptive pills, vaginal ring, injectables, implants and intrauterine devices (IUDs) such as Mirena® by WOCBP subject or male subject's WOCBP partner
- IUDs, such as ParaGard®
- Tubal ligation
- Vasectomy
- Complete abstinence*

*Complete abstinence is defined as complete avoidance of heterosexual intercourse and is an acceptable form of contraception for all study drugs. Female subjects must continue to have pregnancy tests. Acceptable alternate methods of highly effective contraception must be discussed in the event that the subject chooses to forego complete abstinence.

LESS EFFECTIVE METHODS OF CONTRACEPTION

- Diaphragm with spermicide
- Cervical cap with spermicide
- Vaginal sponge
- Male condom without spermicide
- Progestin only pills by WOCBP subject or male subject's WOCBP partner
- Female condom*

* A male and female condom must not be used together

3.3.2 *Exclusion Criteria*

1) Target Disease Exceptions

- a) Subjects with known or suspected central nervous system (CNS) metastases or with the CNS as the only site of disease are excluded. Subjects with CNS lymphoma are excluded. However, subjects with controlled brain metastases will be allowed to enroll. Controlled brain metastases are defined as no radiographic progression for at least 4 weeks following radiation and/or surgical treatment (or 4 weeks of observation if no intervention is clinically indicated), and off of steroids for at least 2 weeks, and no new or progressive neurological signs and symptoms. Please note: for SCCHN subjects with direct extension of tumor through the base of skull will not be excluded as they are considered distinct from hematogenously spread parenchymal brain metastasis.
- b) Ocular melanoma
- c) Participation in any prior clinical study with ipilimumab, or with nivolumab including subjects in comparator arms, in which overall survival is listed as the primary or co-primary endpoint and which has not completed analysis based on the primary endpoint. Exception: I-O experienced NSCLC and melanoma cohort (prior antibody therapy of anti-CTLA-4 and/or anti-PD-1 or anti-PDL-1).
- d) Subjects who have received nivolumab are not eligible to be enrolled with the exception for those NSCLC and MEL subjects enrolling in the expansion cohorts where prior anti-PD-1 or anti-PD-L1 therapies are specifically required.

2) Medical History and Concurrent Diseases

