- iii) History of alcoholic or non-alcoholic steatohepatitis (NASH), auto-immune hepatitis, or previous grade 3-4 drug-related hepatitis) or any form chronic liver disease will be excluded.
- g) Evidence of active infection \leq 7 days prior to initiation of study drug therapy (does not apply to viral infections that are presumed to be associated with the underlying tumor type required for study entry).
- h) Evidence or history of active or latent tuberculosis infection including PPD recently converted to positive; chest x-ray with evidence of infectious infiltrate; recent unexplained changes in fever/chill patterns.
 - i) Any significant acute or chronic medical illness.
 - j) Any major surgery within 4 weeks of study drug administration.
 - k) Subjects who are unable to undergo venipuncture and/or to tolerate venous access.
 - l) Known current drug or alcohol abuse
 - m) Any other sound medical, psychiatric and/or social reason as determined by the investigator.

3) Prohibited Prior Treatments and/or Therapies

- a) Prior therapy with immune checkpoint inhibitors (eg, anti-PD-1, anti-PD-L1, anti-LAG-3); immune costimulatory molecules (eg, anti-CD137, anti-OX40, anti-GITR); anti-cancer vaccines (eg, Provenge, MAGE-3); or other immune modulating monoclonal antibodies. Prior anti-CTLA4 is permitted. Prior anti-PD-1/anti-PD-L1 therapy is permitted for the NSCLC cohort described in Protocol inclusion criteria 2(a)(ii)(1)(e) above.
- b) Subjects who have received prior anti-CTLA4 therapy:
 - i) Prior anti-CTLA4 therapy within 100 days from the first day of study therapy.
 - ii) Subjects who have received prior anti-CTLA4 blockade and experienced the following immune-mediated adverse events:
 - (1). Grade 3 or > pneumonitis, hepatitis, colitis, ocular events;
 - (2). Any CNS event regardless of severity;

(3). Any immune-mediated adverse event requiring additional immunosuppressive therapy beyond steroids for management.

- c) Any anti-cancer therapy (eg, chemotherapy, biologics, vaccines, radiotherapy, or hormonal treatment) including investigational drugs within 4 weeks prior to the first dose of study drug administration, with the exception of GnRH agonist therapy for subjects with prostate cancer. Prior palliative or targeted radiotherapy must have been completed at least 2 weeks prior to the first dose of study drug.

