- l) Subjects who experienced prior non-life threatening checkpoint therapy-related immune-mediated adverse events must have confirmed recovery (resolve to baseline or Grade 1) from these events at the time of study entry, as documented by improvement of clinical symptoms, abnormal findings on physical examination, and/or associated laboratory abnormalities.

4) Physical and Laboratory Test Findings

- a) Known history of testing positive for human immunodeficiency virus (HIV) or known acquired immunodeficiency syndrome (AIDS). Note: Testing for HIV must be performed at sites where mandated by local requirements.
- b) Positive tests for hepatitis B virus surface antigen, hepatitis B core antibody, or hepatitis C RNA (Subjects with positive hepatitis C antibody and negative quantitative hepatitis C by PCR are eligible.) Additional testing or substitute testing per institutional guidelines to rule out infection is permitted.

5) Allergies and Adverse Drug Reaction

- a) History of allergy to components of urelumab or nivolumab, (eg, history of severe hypersensitivity reactions to drugs formulated with polysorbate 80).

6) Sex and Reproductive Status

- a) Women who are pregnant or are breastfeeding.

7) Other Exclusion Criteria

- a) Prisoners or subjects who are involuntarily incarcerated.
- b) Subjects who are compulsorily detained for treatment of either a psychiatric or physical (eg, infectious disease) illness.

Eligibility criteria for this study have been carefully considered to ensure the safety of the study subjects and to ensure that the results of the study can be used. It is imperative that subjects fully meet all eligibility criteria.

3.3.3 *Women of Childbearing Potential*

Women of childbearing potential (WOCBP) is defined as any female who has experienced menarche and who has not undergone surgical sterilization (hysterectomy or bilateral oophorectomy) and is not postmenopausal. Menopause is defined as 12 months of amenorrhea in a woman over age 45 in the absence of other biological or physiological causes. In addition, females under the age of 55 years must have a documented serum follicle stimulating hormone, (FSH) level > 40 mIU/mL to confirm menopause.

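### Exclusion 3(a) exempts only the pretreated NSCLC cohort from its ban on prior anti-PD-1/PD-L1, so as written it shuts out the whole melanoma cohort that requires that therapy

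*Protocol*

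**What the plan says.** Exclusion 3(a) in Protocol 3.3.2 lists as prohibited "Prior therapy with immune checkpoint inhibitors (eg, anti-PD-1, anti-PD-L1, anti-LAG-3", together with costimulatory agents, cancer vaccines and other immune-modulating antibodies. Two reliefs follow. One covers prior anti-CTLA4. The other covers prior anti-PD-1/PD-L1 and is confined to one cohort: "Prior anti-PD-1/anti-PD-L1 therapy is permitted for the NSCLC cohort described in Protocol inclusion criteria 2(a)(ii)(1)(e) above".

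Protocol 3.3.1 defines two expansion cohorts that require such treatment: NSCLC cohort (e), through item (e)(vi), and melanoma cohort (g). For the latter, item (g)(iii) states: "Must have received anti-PD-1/anti-PD-L1 with or without anti-CTLA4 treatment as most recent therapy and have progressed during or after therapy". Item (g)(v) then limits primary refractory patients: "No more than 25% of MEL subjects (5 during stage 1 and 5 during stage 2 of cohort expansion) will be enrolled" with that status. Table 3.1.6-1 gives the cohort its own row, with both stages.

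Two other exclusions in 3.3.2 carry exceptions that do name melanoma:

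- 1(c), on earlier participation in certain ipilimumab or nivolumab trials: "Exception: I-O experienced NSCLC and melanoma cohort (prior antibody therapy of anti-CTLA-4 and/or anti-PD-1 or anti-PDL-1".
- 1(d), on earlier nivolumab: "with the exception for those NSCLC and MEL subjects enrolling in the expansion cohorts where prior anti-PD-1 or anti-PD-L1 therapies are specifically required".

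On discretion, Protocol 3.3 says "No exceptions will be granted", and the end of the exclusion list says "It is imperative that subjects fully meet all eligibility criteria".

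**The concern.** One criterion demands a treatment history that another forbids, and the exception meant to settle the clash names only one of the two cohorts it affects. A site applying the text has two options. It can refuse every candidate for cohort (g), or it can enrol each of them against 3(a) and carry an eligibility violation for each.

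Sites could also resolve the conflict differently from one another, which would give inconsistent screening and needless deviation reports in a cohort that the sponsor added deliberately.

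**Working it through.** No probability calculation is involved. The check sets the criteria side by side and then looks for any other text that removes the conflict.

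**Step 1: which cohorts need prior anti-PD-1/PD-L1, and which exclusions exempt them**

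| Exclusion (Protocol 3.3.2) | What it bars | NSCLC cohort (e) exempt? | Melanoma cohort (g) exempt? |
|---|---|---|---|
| 1(c) | Certain earlier ipilimumab or nivolumab trials | Yes | Yes |
| 1(d) | Earlier nivolumab | Yes | Yes |
| 3(a) | Earlier checkpoint inhibitors, including anti-PD-1/PD-L1 | Yes | **No** |

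Two cohorts require the therapy. Exclusions 1(c) and 1(d) each exempt 2 of 2; 3(a) exempts 1 of 2.

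**Step 2: the logic for cohort (g)**

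- By (g)(iii), every patient in the cohort has had anti-PD-1/PD-L1.
- By 3(a), every patient who has had anti-PD-1/PD-L1 and is not in cohort (e) is excluded.
- A patient in (g) has melanoma and so is not in (e).
- The set of patients meeting both criteria is therefore empty.

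**Step 3: does any other text lift 3(a) for cohort (g)?**

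- The anti-CTLA4 relief inside 3(a) does not help. (g)(iii) makes anti-CTLA4 optional and anti-PD-1/PD-L1 compulsory.
- The exceptions in 1(c) and 1(d) are attached to their own bars and do not refer to 3(a).
- Exclusions 3(k) and 3(l) set conditions for patients who had toxicity on earlier immune therapy. They assume that some such patients enrol, which cohort (e) and the anti-CTLA4 relief already explain, and they exempt nobody from 3(a).
- Protocol 3.3 closes off individual waivers.
- The SAP does not resolve it. Its cohort table (Table 5) has no pretreated melanoma row, and its amendment table (Table 6) ends at Amendment 05.

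**Step 4: number of patients affected**

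Table 3.1.6-1 gives up to about 20 + 20 = 40. The cap in (g)(v) agrees: 5 per stage at 25% is 5 / 0.25 = 20 per stage.

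**Step 5: is this only a difference from the amendment log?**

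No. Both conflicting sentences are current protocol text. The document history helps only on intent and timing: Amendment 06 (09-May-2016) added NSCLC and melanoma patients with earlier anti-PD-1/PD-L1, and Administrative Letter 05 (01-Jun-2016) describes an exception for both tumor types.

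**Step 6: a secondary point in the SAP**

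The entry-deviation list in SAP 7.2.3 flags earlier nivolumab and cites exclusion 1d, but does not repeat the exception found in the current 1(d). If the bullet is programmed literally, an NSCLC-PROG patient whose required earlier therapy was nivolumab would be listed as a deviation. If the programmer applies the cited criterion, that patient would not be. The documents do not say how many such patients there are, so this cannot be sized. The SAP covers amendments only to 22-Dec-2015, so both this omission and the absence of cohort (g) may be version lag.

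**The case against.** The best counter-argument is that nobody would be misled. Exclusion 1(d) itself speaks of melanoma patients in cohorts where earlier anti-PD-1/PD-L1 is required. The cohort has its own heading, a washout rule in (g)(iv), a cap in (g)(v) and a row in the expansion table. A sensible site would let the specific inclusion rule prevail over a general exclusion that was not updated. On this view, wholesale refusal of the cohort is the least likely outcome.

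The point about intent stands, and it lowers the practical risk. It does not repair the text. Cohort (e) also requires the therapy through its own inclusion criteria, yet 3(a) still gives it an express exception. If inclusion criteria overrode 3(a) automatically, that sentence would be unnecessary. Naming (e) alone implies that (g) is not covered, and the no-waiver rule leaves a site no stated way round it.

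Three narrower objections also have force:

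- Forty is a ceiling. Stage 2 normally opens only after at least 4 responses in 20 (Protocol 3.1.6.1), and the documents do not give enrolment in (g) to date.
- The programmed entry list in SAP 7.2.3 cites exclusions 1d, 3b and 3c but not 3a, so it would not itself flag the conflict. The separate route in 7.2.3 for other relevant or significant deviations still could.
- The SAP remarks compare documents that reflect different protocol versions. They are secondary, and the main point does not depend on them.

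**Conclusion.** The concern holds. Taken as written, exclusion 3(a) and inclusion (g)(iii) cannot both be met, so 0 of the up to about 40 planned patients in the pretreated melanoma cohort are eligible. The figure of 40 assumes that both stages fill; with Stage 1 alone it is up to about 20.

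The conclusion rests on reading each exception as applying only to the exclusion it belongs to, which is how the protocol is drafted. The likely cause is an exception that was not extended when cohort (g) was added.

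The consequence is confined to eligibility and deviation reporting. No estimate, sample size or analysis population changes. It should still be corrected, because the conflict lies in an operative entry rule and covers an entire planned cohort.

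**What to change.** Reconcile exclusion 3(a) with inclusion (g)(iii) and exclusions 1(c) and 1(d). One way is to word the 3(a) exception so that it covers every expansion cohort in which prior anti-PD-1/PD-L1 is required, instead of citing cohort (e) alone. The cost is one protocol sentence.

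At the next SAP update, add the exception from 1(d) to the prior-nivolumab bullet in 7.2.3 (one clause), and add cohort (g) to the cohorts the SAP lists. None of this needs extra patients, visits or data.

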3.4.2.1 Permitted Therapy

Subjects are permitted the use of topical, ocular, intra-articular, intranasal, and inhalational corticosteroids (with minimal systemic absorption).

Immunosuppressive agents and the use of systemic corticosteroids are permitted in the context of treating adverse events. Subjects receiving corticosteroids for treatment of drug-related adverse events must be at < 10 mg/day prednisone or equivalent prior to re-initiation of study therapy. Treatment with a short course of steroids (< 5 days) up to 7 days prior to initiating study drug is permitted. A brief course of corticosteroids for prophylaxis (eg, contrast dye allergy) or for treatment of non-autoimmune conditions (eg, delayed-type hypersensitivity reaction caused by a contact allergen) is permitted.

Subjects receiving corticosteroid treatment for adverse events from prior immunotherapy must have completed steroid tapers for treatment of these adverse events by a minimum of 14 days prior to commencing treatment with study therapy.

Subjects may continue to receive hormone replacement therapy.

RANK-L inhibitors and bisphosphonates are permitted as clinically indicated but should be avoided, if possible, prior to completion of cycle 1.

Palliative and supportive care for disease related symptoms may be offered to all subjects on the trial after the DLT evaluation period. Limited radiation therapy or surgery to control isolated lesions is permitted for subjects who have investigator assessed clinical benefit following consultation with the BMS Medical Monitor. Subjects should not receive study treatment during radiation or surgery.

3.5 Discontinuation of Subjects from Treatment

Subjects MUST discontinue investigational product (and non-investigational product at the discretion of the investigator) for any of the following reasons:

- Subject's request to stop study treatment and/or participation in the study;
- Any clinical adverse event (AE), laboratory abnormality, or intercurrent illness which, in the opinion of the investigator indicates that continued participation in the study is not in the best interest of the subject;
- Termination of the study by Bristol-Myers Squibb (BMS);
- Loss of ability to freely provide consent through imprisonment or involuntary incarceration for treatment of either a psychiatric or physical (eg, infectious disease) illness;
- Pregnancy;
- Documented and confirmed disease progression as defined by RECIST or IWG criteria (see Appendices 1 and 2) unless subject meets criteria for treatment beyond progression (See [Section 3.5.1](#));
- Clinical deterioration while receiving active study therapy that in the opinion of the investigator indicates that continued participation in the study is not in the best interest of the subject;
- Discretion of the investigator;
- Inability to comply with the protocol requirements;
- Protocol defined reasons for discontinuation (see [Section 4.5.7](#)).

The investigator must notify the BMS Medical Monitor/designee in the event a female subject becomes pregnant within 24 hours and submit information to WWS on the pregnancy form within 24 hours. The study drug should be discontinued after pregnancy has been confirmed.

All subjects who discontinue should comply with protocol specified follow-up procedures as outlined in [Table 5.1-3](#). The only exception to this requirement is when a subject withdraws consent for all study procedures or loses the ability to consent freely (ie, is imprisoned or involuntarily incarcerated for the treatment of either a psychiatric or physical illness).

If study drug is discontinued prior to the subject's completion of the study, the reason for the discontinuation must be documented in the subject's medical records and entered on the appropriate case report form (CRF) page.

3.5.1 Treatment Beyond Disease Progression

As described in [Section 1.1.2](#) accumulating evidence indicates a minority of subjects with solid tumors treated with immunotherapy may derive clinical benefit despite initial evidence of PD. Subjects will be permitted to continue on treatment beyond initial RECIST 1.1 defined PD, or progression defined by relapsed disease (after CR) or progressive disease (after PR, SD) per 2007 IWG criteria, as long as they meet the following criteria:

- Investigator-assessed clinical benefit, and do not have rapid disease progression;
- Continue to meet all other study protocol eligibility criteria;
- Tolerance of study drug;
- Stable performance status;
- Treatment beyond progression will not delay an imminent intervention to prevent serious complications of disease progression (eg, CNS metastases);
- Subject provides written informed consent prior to receiving any additional urelumab/nivolumab treatment, using an ICF describing any reasonably foreseeable risks or discomforts, or other alternative treatment options.

The assessment of clinical benefit should take into account whether the subject is clinically deteriorating and unlikely to receive further benefit from continued treatment. All decisions to continue treatment beyond initial progression must be discussed with the BMS Medical Monitor and an assessment of the risk/benefit of continuing with study therapy must be documented in the study records. Subjects will be re-consented to explain the rationale for this ongoing treatment.

3.5.1.1 Discontinuation due to further progression

Subjects should discontinue study therapy upon further evidence of further progression, defined as an additional 10% or greater increase in tumor burden volume from time of initial progression (including all target lesions and new measurable lesions).

The tumor burden volume from time of initial progression should be used as the reference baseline for comparison with the post-progression assessment.

Any new lesion considered non-measurable at the time of initial progression may become measurable and therefore must be included in the tumor burden measurement as follows:

For solid tumors: New lesions are considered measurable at the time of initial progression if the longest diameter is at least 10 mm (except for pathological lymph nodes, which must have a short axis of at least 15 mm).

For B-cell NHL: New lesions are considered measurable at the time of initial progression if the long axis is more than 15 mm regardless of the short axis. If a lymph node has a long axis of 11 to 15 mm, it should only be considered measurable if its short axis is more than 10 mm.

For statistical analyses that include the investigator-assessed progression date, subjects who continue treatment beyond initial investigator-assessed, RECIST 1.1-defined progression will be

considered to have investigator-assessed progressive disease at the time of the initial progression event.

3.5.1.2 *Assessment schedule for the subjects with post-progression treatment*

Subjects should continue to receive monitoring according to the On-Treatment Assessments in **Table 5.1-2** and **Table 5.1-5**. Radiographic assessment by CT (preferred) or MRI described in **Section 5.4** and **Table 5.1-2** are required when subjects continue post-progression treatment. For subjects with B-cell NHL, study termination can be based on investigator-assessed evidence of clinical progression. FDG-PET scans for subjects with B-cell NHL are not mandated after investigator-assessed progression, but can be performed and results collected.

For subjects that discontinue post-progression treatment, no additional radiographic assessments will be required.

[REDACTED]

3.6.1 *Withdrawal of Consent*

Subjects who request to discontinue study drug will remain in the study and must continue to be followed for protocol specified follow-up procedures. The only exception to this is when a subject specifically withdraws consent for any further contact with him/her or persons previously authorized by subject to provide this information. Subjects should notify the Investigator of the decision to withdraw consent from future follow-up **in writing**, whenever possible. The withdrawal of consent should be explained in detail in the medical records by the investigator, as to whether the withdrawal is from further treatment with study drug only or also from study procedures and/or post treatment study follow-up, and entered on the appropriate CRF page. In the event that vital status (whether the subject is alive or dead) is being measured, publicly available information should be used to determine vital status only as appropriately directed in accordance with local law.

3.6.2 *Lost to Follow-Up*

All reasonable efforts must be made to locate subjects to determine and report their ongoing status. This includes follow-up with persons authorized by the subject as noted above. Lost to follow-up is defined by the inability to reach the subject after a minimum of three documented phone calls, faxes, or emails as well as lack of response by subject to one registered mail letter. All attempts

should be documented in the subject's medical records. If it is determined that the subject has died, the site will use permissible local methods to obtain the date and cause of death.

If investigator's use of a third-party representative to assist in the follow-up portion of the study has been included in the subject's informed consent, then the investigator may use a Sponsor-retained third-party representative to assist site staff with obtaining subject's contact information or other public vital status data necessary to complete the follow-up portion of the study. The site staff and representative will consult publicly available sources, such as public health registries and databases, in order to obtain updated contact information. If after all attempts, the subject remains lost to follow-up, then the last known alive date as determined by the investigator should be reported and documented in the subject's medical records.

